3.2.1.7 Optional Biomarker

For subjects consenting to the optional biomarker samples, blood and urine will be collected at the End of Study Visit for the evaluation of biomarkers. These samples will be shipped to the central laboratory for processing and storage prior to analysis. Subjects who do not wish to participate in the optional biomarker research may still participate in the clinical study.

3.2.1.8 Optional Pharmacogenomic

For subjects consenting to pharmacogenomic analysis, blood samples will be collected at the End of Study Visit for pharmacogenomics analyses. These samples will be shipped to the central laboratory for processing and storage prior to analysis. Genetic variants and/or gene expression patterns will be analyzed to evaluate their association with observed clinical response and

tolerability to prostacyclin therapy. Subjects who do not wish to participate in the optional pharmacogenomic research may still participate in the clinical study.

3.2.2 Safety

3.2.2.1 Medical History and Physical Examinations

A complete medical history, demographics, PAH history, and physical examination will be conducted during the Screening period. Significant past or present illnesses, current prescription or nonprescription medications (including vitamins and herbal products), and history of allergies or idiosyncratic responses to drugs should be noted in the eCRF. Any significant changes to the subject's medical condition, physical examination, and concomitant medications must be documented throughout the course of the study. A complete physical examination will be conducted at the Study Drug Termination Visit.

3.2.2.2 Clinical Laboratory Tests

Clinical laboratory tests will be assessed at the Screening and Baseline visits prior to starting study drug. Screening and Baseline clinical laboratory assessments can be combined into a single blood draw if all eligibility criteria are met within 48 hours prior to randomization. Central laboratory data are ultimately used to qualify patients for the study. However, for patients who are well known to the Investigator and who are clinically stable, the Investigator may choose not to delay randomization while waiting for central laboratory confirmation of local laboratory values. Clinical laboratory assessments will also be assessed at Weeks 12 and 24, at the first Continued Visit, and every other Continued Visit thereafter (i.e., Continued Visits #3, #5, #7, etc.) as displayed in Appendix 15.3. Clinical laboratory tests will also be assessed at the Study Drug Termination visit.

A urine pregnancy test will be collected at Screening, Baseline, Weeks 4, 8, 12, 24, every 12 weeks thereafter, and at the Study Drug Termination Visit for women of child bearing potential (WOCBP). Screening and Baseline urine pregnancy tests can be combined into a single test if all eligibility criteria are met within 48 hours prior to randomization.

3.2.2.3 Vital Signs

Vital signs will be assessed at Screening and Baseline prior to starting study medication and at Weeks 4, 8, 12, and 24. After Week 24, vital signs will be assessed every 12 weeks and at the Study Drug Termination Visit. All vital signs will be collected prior to or at least 30 minutes following the corresponding 6MWT. Vital signs include blood pressure, peripheral (radial/brachial artery) heart rate, respiration rate, and weight. Height will be collected at the Baseline visit. Vital signs must be collected following at least 5 minutes of rest (or at least 30 minutes after a 6MWT) to ensure accurate measurement.

3.2.2.4 Adverse Events

AEs will be captured from the time the ICF is signed. All AEs should be followed until either resolution (or return to normal or Baseline values), until they are judged by the Investigator to no longer be clinically significant, or for up to 30 days if the AE extends beyond the final visit. All SAEs should be followed until resolution, death, or the subject is lost to follow-up even if they are ongoing more than 30 days after completion of the final visit. Sections 9 and 15.4 provide the guidelines and definitions for recording AEs.

Symptoms of PAH (disease related events) should only be recorded as an AE if the event is either serious, new, or unusual with respect to intensity, frequency, duration as compared to symptoms in the subject's medical history; or there is a reasonable possibility that the event was caused by the study drug.

3.2.2.5 12-Lead ECG

Twelve-lead ECGs will be recorded after at least 5 minutes rest in the semi-recumbent position at Screening, Week 24, and at the Study Drug Termination Visit. Recordings should include lead II as a rhythm strip and contain at least five QRS complexes. ECG parameters collected include heart rate, PR interval, QT interval, QRS duration, and any clinically significant abnormalities.

3.3 NUMBER OF CENTERS

The study is an international multi-center study with approximately 150 centers participating.

3.4 NUMBER OF SUBJECTS

At least 610 subjects with a maximum of 850 subjects will be randomized (1:1 UT-15C: placebo) across all sites participating in the study in order to obtain the required number of adjudicated clinical worsening (morbidity and mortality) events.

3.5 ESTIMATED STUDY DURATION

Subjects will remain in the study until they either experience a clinical worsening event, discontinue the study for any other reason, or approximately 205 adjudicated clinical worsening events have occurred. It is estimated that the overall study duration will last for 4 years; however, this is dependent on the rate of clinical worsening events.

Subjects that discontinue and do not roll into the open-label extension study (TDE-PH-311) will be contacted approximately 30 days (± 5 days) after study drug discontinuation to confirm their survival status. Subjects that complete TDE-PH-310 and roll in to the open-label extension study will also be contacted approximately 30 days (± 5 days) after study drug discontinuation in study TDE-PH-310 to confirm their survival status.

Subjects may also continue to be contacted after the final study visit to assess ongoing AEs/SAEs (see Section 9.2 for additional details).

4 SUBJECT ELIGIBILITY

Inclusion and exclusion criteria are to be assessed during the Screening period and reconfirmed at the Baseline visit prior to randomization. If necessary, certain procedures may be conducted during the Screening period after obtaining informed consent to determine subject eligibility for the study.

4.1 INCLUSION CRITERIA

A subject is eligible for inclusion in this study if all of the following criteria apply:

1. The subject voluntarily gives informed consent to participate in the study.
2. The subject is 18 to 75 years of age (inclusive) at Screening (i.e., date of providing written informed consent).
3. Women of child bearing potential (WOCBP) includes any female who has experienced menarche and who has not undergone successful surgical sterilization (hysterectomy, bilateral tubal ligation or bilateral oophorectomy) or is not postmenopausal (defined as

amenorrhea for at least 12 consecutive months). Women of childbearing potential must practice true abstinence from intercourse when it is in line with their preferred and usual lifestyle, or use two different forms of highly effective contraception for the duration of the study, and for at least 30 days after discontinuing study medication. Medically acceptable forms of effective contraception include: (1) approved hormonal contraceptives (such as birth control pills), (2) barrier methods (such as a condom or diaphragm) used with a spermicide, (3) an intrauterine device (IUD), or (4) partner vasectomy. For women of childbearing potential, a negative urine pregnancy test is required at Screening and Baseline prior to initiating study medication.

4. The subject, if male, must use a condom during the length of the study, and for at least 48 hours after discontinuing study medication.
5. The subject has a diagnosis of symptomatic idiopathic or heritable PAH, PAH associated with CTD, PAH associated with HIV infection, PAH associated with repaired congenital systemic-to-pulmonary shunt (at least 1 year since repair with respect to the date of providing informed consent) or PAH associated with appetite suppressant or toxin use.
6. The subject, if known positive for HIV infection, has a CD4 lymphocyte count of at least 200 cells/mm³ assessed at Screening and is receiving current standard of care anti-retroviral or other effective medication for treatment of HIV infection.
7. The subject must have a Baseline 6MWD greater than or equal to 150 meters, in the absence of a concurrent injury, illness (other than PAH or a PAH related condition), or other confounding factor including, but not limited to, use of an aid for ambulation (e.g., use of a cane or walker) or connection to a non-portable machine, that would prevent the accurate assessment of the subject's exercise capacity.
8. The subject must be optimally treated with conventional pulmonary hypertension therapy (e.g., oral vasodilators, oxygen, digoxin, diuretics, anticoagulants as deemed appropriate by the Investigator) with no additions, discontinuations, or dose changes for a minimum of 10 days prior to randomization. The exceptions are the discontinuation or dose changes of anticoagulants and/or dose change of diuretics.
9. The subject must have been receiving a PAH-approved oral monotherapy at a minimum dose that complies with the approved prescribing information for the product for at least 30 days prior to randomization and must have been receiving a stable dose for at least 10 days prior to randomization. The subject who previously received two PAH-approved oral therapies at the same time (specifically, a PDE5-I, an ERA, or an sGC stimulator) will be eligible provided they received these medications concomitantly for less than or equal to 90 days cumulatively. The subject must have taken only one PAH-approved therapy for at least 30 days prior to randomization and must have been receiving a stable dose for at least 10 days prior to randomization.
10. The subject has previously undergone a cardiac catheterization either within three years prior to the start of screening, or during the screening period, and the most recent assessment has documented a mean pulmonary artery pressure (PAPm) of at least 25 mmHg, a pulmonary capillary wedge pressure (PCWP) (or in the event a PCWP cannot be reliably obtained, a left ventricular end diastolic pressure [LVEDP]) less than or equal to 15 mmHg, and absence of unrepaired congenital heart disease (other than patent foramen ovale [PFO]). In the event that a reliable PCWP or LVEDP are unable to

be obtained during cardiac catheterization, subjects with clinically normal left heart function and absence of clinically relevant mitral valve disease on echocardiography are eligible for enrollment.

11. The subject has undergone echocardiography with evidence of clinically normal left systolic and diastolic ventricular function and absence of any clinically significant left sided heart disease (e.g. mitral valve disease). Subjects with clinically insignificant left ventricular diastolic dysfunction due to the effects of right ventricular overload (i.e., right ventricular hypertrophy and/or dilatation) are eligible.
12. The subject has a previous ventilation perfusion lung scan, and/or high resolution computerized tomography scan of the chest, and/or pulmonary angiography that are consistent with the diagnosis of PAH (e.g., low probability of pulmonary embolism; absence of major perfusion defects).
13. The subject has pulmonary function tests conducted within 6 months before screening or during the Screening period to confirm the following:
 - a. Total lung capacity (TLC) is at least 60% (predicted value) assessed by either whole body plethysmography or helium dilution or nitrogen washout technique
 - b. Forced expiratory volume at one second (FEV₁) of at least 50% (predicted value)
14. In the opinion of the Principal Investigator, the subject is able to communicate effectively with study personnel, and is considered reliable, willing and likely to be cooperative with protocol requirements, including attending all study visits.

4.2 EXCLUSION CRITERIA

A subject is not eligible for inclusion in this study if any of the following criteria apply:

1. The subject is pregnant or lactating.
2. The subject has previously received UT-15C.
3. The subject has received a PGI₂, (except if used during acute vasoreactivity testing) within 30 days prior to randomization or had previous intolerance or significant lack of efficacy to any PGI₂, or PGI₂ analogue, that resulted in discontinuation or inability to titrate that therapy effectively.
4. The subject has had any background conventional therapies for PAH added, removed or dose adjusted (including but not limited to oxygen, vasodilators, diuretics, digoxin, anticoagulants) within 10 days prior to randomization. The exceptions are removal or dose adjustments of anticoagulants and/or dose adjustments of diuretics.
5. The subject has received their first dose of a PAH-approved therapy less than 30 days prior to randomization, or has had their PAH-approved oral monotherapy dose changed within 10 days prior to Randomization, or the subject discontinued any PAH-approved therapy within 30 days prior to Screening, or the subject previously received two PAH-approved oral therapies at the same time (specifically, a PDE5-I, an ERA, or an sGC stimulator) concomitantly for more than 90 days cumulatively.
6. The subject has any disease associated with PAH other than CTD, HIV infection, repaired (for at least one year) congenital systemic-to-pulmonary shunt, PAH associated

with appetite suppressant/toxin use (e.g., portal hypertension, chronic thromboembolic disease, pulmonary veno-occlusive disease, etc.) or has had an atrial septostomy.

7. The subject has a current diagnosis of uncontrolled sleep apnea as defined by their physician.
8. The subject has a history of ischemic heart disease, including a previous myocardial infarction or symptomatic coronary artery disease within 6 months prior to Screening or a history of left sided myocardial disease as evidenced by a mean PCWP (or a left ventricular end diastolic pressure [LVEDP]) greater than 15 mmHg or left ventricular ejection fraction less than 40% as assessed by either multigated angiogram (MUGA), angiography, or echocardiography.
9. The subject has uncontrolled systemic hypertension as evidenced by systolic blood pressure greater than 160 mmHg or diastolic blood pressure greater than 100 mmHg.
10. The subject has ALT or AST levels at least greater than 3 times the upper limit of normal, clinically significant liver disease/dysfunction, or known Child-Pugh Class C hepatic disease (Appendix 15.5) at Screening.
11. The subject has any other disease or condition that would interfere with the interpretation of study assessments.
12. The subject has a musculoskeletal disorder (e.g., arthritis affecting the lower limbs, recent hip or knee joint replacement, artificial leg), is using a device to assist walking (e.g. cane or walker), or any disease that is likely to limit ambulation, or is connected to a machine that is not portable.
13. The subject has an unstable psychiatric condition or is mentally incapable of understanding the objectives, nature, or consequences of the trial, or has any condition which in the Investigator's opinion would constitute an unacceptable risk to the subject's safety.
14. The subject is receiving an investigational drug, has an investigational device in place, or has participated in an investigational drug or device study within 30 days prior to Screening.
15. The subject has chronic renal insufficiency as defined by either a Screening creatinine value greater than 2.5 mg/dL (221 $\mu\text{mol/L}$) or the requirement for dialysis.
16. Subjects must not have 3 or more of the following left ventricular disease/dysfunction risk factors:
 - i. Body Mass Index (BMI) $\geq 30 \text{ kg/m}^2$
 - ii. History of essential hypertension
 - iii. Diabetes mellitus – any type
 - iv. Historical evidence of significant coronary disease established by any one of: history of myocardial infarction or percutaneous coronary intervention or angiographic evidence of coronary artery disease (>50% stenosis in at least one coronary artery), positive stress test with imaging, previous coronary artery bypass graft, stable angina

4.3 PRESCRIBED THERAPY**4.3.1 PAH-Approved Therapies**

All subjects must be receiving a dose of one PAH-approved oral therapy that complies with the approved prescribing information (as described in [Table 4-1](#)) for the product for a minimum of 30 days and at the current dose for at least 10 days prior to randomization. All subjects must be willing to remain on the same background approved PAH oral therapy at the same dose for the duration of the study. In the event a subject must undergo a change in background therapy, they should be switched to another approved agent in the same medication class if possible. If another agent in the same class is not available, the subject should be switched to an agent from another class of approved PAH oral medications. If no alternative therapy is available, the subject will continue in the study until either a clinical worsening event has occurred, the subject withdraws from the study, or the study is completed/discontinued.

Table 4-1 Minimum Allowable Doses of Background PAH Oral Therapy

PAH-Approved Background Therapy	Dosing Schedule
ambrisentan	5 mg once daily
bosentan*	125 mg twice daily
macitentan	10 mg once daily
sildenafil	20 mg three times daily
tadalafil**	40 mg once daily
riociguat***	1 mg three times daily

* 62.5 mg twice daily is permitted if used per prescribing guidelines (e.g., subject weighs less than 40 kg or has elevated liver function tests)

** 20 mg once daily is permitted if used per prescribing guidelines (e.g., subject has mild or moderate renal insufficiency)

***0.5 mg three times daily permitted if used per prescribing guidelines (e.g. subject cannot tolerate hypotensive effects)

Prior to Week 24, if the Investigator, for any reason, initiates a second PAH-approved oral therapy in addition to the PAH-approved oral therapy initiated prior to Screening (e.g., due to disease progression without meeting the definition of clinical worsening as defined in [Section 2.1](#)), the subject must be discontinued from the study drug. The subject should be encouraged to remain in the study and attend all visits up to and including Week 24; however, the subject will not be eligible for enrollment in the open-label study (TDE-PH-311). After Week 24, if the Investigator initiates a second PAH-approved oral therapy due to any reason in addition to the PAH-approved oral therapy initiated prior to Screening, the subject must be discontinued from the study and will not be eligible for enrollment in the open-label study.

All changes in drug or dosage regimens during the study will be recorded in the subject's source documents and transcribed as required to the eCRF.

Product labeling for the background PAH-approved oral therapy should be consulted in order to guide the monitoring of AEs. The dose of study drug should be adjusted first in response to any new AEs that occur during the study, rather than adjusting the dose of PAH-approved oral therapy; unless the event is considered causally related to the PAH-approved oral therapy. If a subject meets the definition of clinical worsening during the study and receives only short term (28 days or less) treatment with an infused or inhaled PGI₂ therapy for worsening PAH, they will be permitted to enter the open-label extension study (TDE-PH-311). If a subject prematurely discontinues the study for any reason other than clinical worsening, or receives long-term (29 days or more) treatment with an infused or inhaled PGI₂ therapy for worsening PAH, they will not be permitted to enter the open-label extension study. During the course of the study, if the Investigator initiates a second PAH-approved oral therapy due to any reason (e.g. disease progression without meeting the definition of clinical worsening as defined in Section 2.1) in addition to the PAH-approved oral therapy initiated prior to Screening, the subject must be discontinued from the study and will not be eligible for enrollment in the open-label study (TDE-PH-311).

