- ^l The Study Termination Visit includes the study drug termination which should be pconducted at the time the decision is made to discontinue the study drug (prior to down titration), either because the subject has met clinical worsening criteria or is being permanently discontinued from the 310 study. The 6MWD should be conducted within 3 to 6 hours after the most recent dose of study medication and preferably before the drug is down titrated (if the subject is being permanently discontinued rather than transitioning to the TDE-PH-311 study)
- ^m If subject permanently discontinues study drug before Week 24 and is ineligible for the TDE-PH-311 study, subject should be encouraged to remain in study and attend visits up to and including Week 24. The end of study assessments (survival status, AE assessment, drug accountability, concomitant medications, etc.) should be conducted after the subject has stopped taking the study medication (before or at Week 24)
- ⁿ Weekly telephone contact should be completed and subject study drug dose must also be recorded at Week 16 and Week 20 in the eCRF. More frequent telephone calls may be necessary depending on the frequency of dose titration and to manage AEs or signs and symptoms of disease
- ^o For subjects consenting to the optional biomarker samples.
- ^p For subjects consenting to the optional pharmacogenomic sample.

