3.2.1.2.2 Baseline Six Minute Walk Test

A Baseline 6MWT must be performed prior to initiation of study drug and should be conducted on the day of randomization. The Baseline 6MWT must be conducted no earlier than 1 day following the practice 6MWT, for applicable subjects. Once the Baseline 6MWT has been

conducted, the site will enter the subject's six-minute walk distance into an interactive voice or web response system (IVRS/IWRS). IVRS/IWRS will confirm to site personnel the subject's eligibility to participate in the study based on 6MWD, and if eligible, randomize the subject into a treatment group and allocate appropriate study drug.

3.2.1.2.3 *Treatment Six-Minute Walk Tests*

6MWTs will be conducted at Weeks 4, 8, 12, 24, and every 12 weeks thereafter. The 6MWT should be conducted 3 to 6 hours following the last dose of study medication. Subjects receiving supplemental oxygen during the Baseline 6MWT must continue to receive the same flow rate and mode of oxygen therapy at all subsequent 6MWT assessments; any changes in oxygen therapy administration should be noted in the eCRF. In addition, subjects receiving pulmonary rehabilitation prior to study entry should continue on the same schedule up to and including Week 24. Following Week 24, pulmonary rehabilitation may be adjusted per standard of care. Pulmonary rehabilitation may not be added to a subject's regimen between randomization and Week 24. Documentation of pulmonary rehabilitation should occur in the special circumstances section of the eCRF. Additional 6MWTs may be conducted as appropriate throughout the course of the study for the purposes of evaluating clinical worsening status.

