Plasma NT-proBNP concentration is a useful biomarker for PAH as it is associated with changes in right heart morphology and function [Fijalkowska 2006]. NT-proBNP sample collection will occur at Baseline (prior to starting study drug), Week 12, Week 24, the first Continued Visit, and every other Continued Visit thereafter (i.e., Continued Visits #3, #5, #7, etc.). NT-proBNP will also be assessed at the Study Drug Termination visit.

3.2.1.6 *Right Heart Catheterization (Optional Assessment)*

This section describes the optional RHC assessments that may be conducted at Baseline and Week 24.

If a subject agrees to participate in the optional hemodynamic assessments, a RHC must be performed within 5 days before randomization (inclusive). The subject must be on stable

background therapy for a minimum of 10 days prior to this RHC. If a RHC is performed on the day of randomization, all other study-related assessments, other than initiation of study drug, should be performed prior to conduct of the RHC. A follow-up RHC must be performed within 72 hours following completion of Week 24 assessments. As best as possible, follow-up RHC should be performed within 3 to 6 hours of previous dose. Hemodynamic parameters to be assessed and recorded include heart rate (HR), systolic systemic arterial pressure (SAPs), diastolic systemic arterial pressure (SAPd), mean systemic arterial pressure (SAPm), systolic pulmonary artery pressure (PAPs), diastolic pulmonary artery pressure (PAPd), mean pulmonary artery pressure (PAPm), mean right atrial pressure (RAPm), mean pulmonary capillary wedge pressure (PCWPm), cardiac output (CO), arterial oxygen saturation (SaO₂), and mixed venous oxygen saturation (SvO₂). Additional hemodynamic parameters may also be calculated based on these measurements (e.g., pulmonary vascular resistance [PVR] and cardiac index [CI]). Weight and height will be collected to calculate body surface area (BSA) and index the cardiac output.

While this section describes the optional RHC assessments at Baseline and Week 24, all subjects eligible to participate in this study must either have data available from a historical RHC conducted within three years prior to the start of screening (i.e., date of signing the Informed Consent Form [ICF]), or undergo a RHC during the screening period prior to randomization with results consistent with the diagnosis of PAH as described in Section 4.1.

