7.4 STUDY DRUG TERMINATION VISIT

Subjects will continue in the study until they experience clinical worsening, prematurely discontinue the study for any reason, or approximately 205 adjudicated clinical worsening events have occurred. If a subject remains ongoing with study treatment at the time when approximately 205 adjudicated clinical worsening events have occurred, the Study Drug Termination Visit should be scheduled as soon as possible. The following assessments will be conducted immediately after the decision is made to discontinue study drug (prior to down titration).

- Vital signs (following at least 5 minutes of rest)
- Physical examination
- Clinical worsening assessment
- WHO Functional Class for PAH
- AE assessment
- Drug accountability/compliance
- 12-lead ECG (following at least 5 minutes rest in the semi-recumbent position)
- Concomitant medications
- 6MWT/Borg dyspnea score (6MWT to be initiated 3 to 6 hours after last dose of study drug and following at least 5 minutes of rest; Borg dyspnea score to be conducted immediately following 6MWT)
- Urine pregnancy test (for WOCBP)
- Clinical laboratory tests/NT-proBNP

- Collection of blood sample for evaluation of blood biomarkers (optional)
- Collection of urine sample for evaluation of urine biomarkers (optional)
- Collection of blood sample for evaluation of pharmacogenomics (optional)

If the subject permanently discontinues study drug prior to Week 24 for any reason other than clinical worsening (e.g., AEs, addition of second PAH-approved oral therapy), the subject should immediately complete the study drug termination visit assessments and be encouraged to remain in the study and complete all visits up to and including Week 24. The Study Drug Termination Visit assessments should be conducted immediately after the decision is made to discontinue study drug (prior to down titration).

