### 9.1 SUBJECT ACCOUNTABILITY

All subjects' disposition information will be listed, including the study population the subjects belong to, whether or not subjects completed the study drug treatment, reason study drug was stopped, whether or not subjects completed at least 24 weeks of study assessments, primary reason for not completing 24 weeks of assessments, whether or not subjects completed the study, reason for not completing the study, and whether or not subjects rolled over to the open-label extension study (TDE-PH-311).

The listing of subject accountability will include dates of informed consent, randomization, first study drug dose, last study drug dose, last dose week, and last assessment week.

Whether subjects received study drug; whether subjects completed the Weeks 4, 8, 12, and 24 assessments, and every 12-week follow-up assessment thereafter; study drug termination status; and study discontinuation status will be summarized by treatment group and overall.

Information regarding whether each subject is included in each analysis population (see Section 6) will be listed. If a subject is not included in a particular analysis population, the reason for exclusion will be noted on the listing. Also noted on the listing will be the

randomized treatment assignment and the actual treatment subjects have received. The summary will include the frequency and percentage of all subjects in each analysis population by treatment group and overall.

All stratification information used in the random assignment of subjects to treatment group (from the central randomization database) will be listed, including date and time of randomization, background PAH therapy, Baseline walk distance category, whether or not the treatment is unblinded, and if so, date/time of blind break. For observations where any stratification information has been corrected, both the original and corrected information will be listed. Background PAH therapy and Baseline walk distance used for randomization stratification will be summarized by treatment group and compared using Fisher's exact test or Wilcoxon rank sum test, as appropriate.

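### Protocol 4.3.1 gives two incompatible rules for a subject who starts a second oral PAH therapy before Week 24: stay for visits through Week 24, or leave the study

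*Protocol*

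**What the plan says.** Four provisions bear on a subject who adds a second PAH-approved oral drug.

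- **Protocol 4.3.1, first paragraph after Table 4-1.** Before Week 24, study drug must stop. For participation: "The subject should be encouraged to remain in the study and attend all visits up to and including Week 24". After Week 24, the same step means removal from the study.
- **Protocol 7.4.** It covers permanent discontinuation of study drug before Week 24 "for any reason other than clinical worsening (e.g., AEs, addition of second PAH-approved oral therapy", so it names this case. Such a subject completes the termination assessments and is to "be encouraged to remain in the study and complete all visits up to and including Week 24".
- **Protocol Table 3-1, note m.** For any subject who permanently stops study drug before Week 24 and cannot enter TDE-PH-311: "subject should be encouraged to remain in study and attend visits up to and including Week 24". It does not name second oral therapy, but these subjects meet both of its conditions.
- **Protocol 4.3.1, last sentence.** It begins "During the course of the study, if the Investigator initiates a second PAH-approved oral therapy due to any reason" and requires that the subject be discontinued from the study. It has no Week 24 split.

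All the 4.3.1 text agrees that such a subject cannot enter the open-label study. The conflict is only about staying in this one. SAP 9.1 also lists "whether or not subjects completed at least 24 weeks of study assessments" as an item separate from completion of study drug, which fits the stay rule.

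**The concern.** A coordinator who reads 4.3.1 to its end finds a mandatory instruction to take the subject out of the study. A coordinator who works from 7.4 or the schedule of events keeps the subject coming to Week 24. Both are following current protocol text, so sites can differ, and no text says which rule yields.

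Week 24 is the time point of all three formally tested secondary endpoints, and the SAP plans one 6MWD analysis that needs visits made after study drug has stopped. The protocol's own example of why a second drug is added is disease progression short of the clinical worsening definition. The missing visits may therefore be related to outcome.

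**Working it through.** The plan states no figure on this point. The check is a comparison of texts, followed by a count of the assessments at stake.

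**1. The rules side by side**

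| Provision | Period covered | Names second oral therapy | Participation |
|---|---|---|---|
| 4.3.1, first paragraph after Table 4-1 | Before Week 24 | Yes | Stop drug; encouraged to attend to Week 24 |
| Same paragraph | After Week 24 | Yes | Must leave study |
| 7.4 | Before Week 24 | Yes, as an example | Drug stopped; encouraged to attend to Week 24 |
| Table 3-1 note m | Before Week 24 | No (general) | Drug stopped; encouraged to attend to Week 24 |
| 4.3.1, last sentence | Whole study | Yes | Must leave study |

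If the last sentence is read as applying only after Week 24, it repeats what the earlier paragraph already says. If it is read as written, it contradicts that paragraph for the period before Week 24. It is either redundant or wrong, so deleting it loses nothing.

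**2. Scheduled assessments at stake per subject**

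Inputs: "6MWTs will be conducted at Weeks 4, 8, 12, 24, and every 12 weeks thereafter" (Protocol 3.2.1.2.3), and "NT-proBNP sample collection will occur at Baseline (prior to starting study drug), Week 12, Week 24, the first Continued Visit" (Protocol 3.2.1.5). Up to Week 24 this gives walks at Weeks 4, 8, 12 and 24, and NT-proBNP at Weeks 12 and 24. For each stopping time, count the visits still to come. Under the last sentence, the count after the termination visit is 0 and 0.

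| Drug stops | Walk tests forgone | NT-proBNP samples forgone |
|---|---|---|
| Before Week 4 | 4 | 2 |
| Weeks 4 to 8 | 3 | 2 |
| Weeks 8 to 12 | 2 | 2 |
| Weeks 12 to 24 | 1 | 1 |

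These are maxima, because the stay rule only encourages attendance.

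**3. What the termination visit supplies**

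Protocol 7.4 collects a walk test and NT-proBNP at the termination visit under either rule. SAP Table 8-1 sets the Week 24 window as 127 < Study Day ≤ 211, with Day 1 the first dosing day. Day 127 is (127 − 1)/7 = 18.0 weeks after first dose.

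- Termination visit on or before Day 127: it gives no value in the Week 24 window.
- Termination visit on Days 128 to 168: its on-drug values fall in the Week 24 window, but the off-drug Week 24 walk is still lost if the subject is removed.

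**4. Analysis by analysis**

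- *6MWD sensitivity analysis with post-termination data (SAP 10.2.1.1).* It is designed to use off-drug walks. Any that the subject would have attended are lost, whatever the day of stopping.
- *NT-proBNP Week 24 ANCOVA (SAP 10.2.2), second in the testing sequence.* Subjects without a valid Week 24 value are excluded. The last sentence changes a subject's inclusion only if three things hold: the termination visit is by Day 127, an off-drug sample counts as valid, and the subject would have attended. The SAP does not settle validity. The supportive LOCF and MMRM analyses (SAP 10.2.2 and 10.3.4) keep subjects with an earlier post-Baseline value.
- *6MWD MMRM (SAP 10.2.1).* It uses observed values to Week 24 without saying whether off-drug walks count. Earlier walks contribute under either rule.
- *Non-parametric 6MWD analysis (SAP 10.2.1).* It excludes walks after study drug termination, so the choice of rule does not affect it.
- *Main primary analysis (SAP 10.1.1.2).* It censors at study drug discontinuation and ignores non-fatal events more than 7 days later. Deaths count up to 30 days after the last dose, and Protocol 3.5 has survival status checked at about 30 days for subjects who leave. The choice of rule makes essentially no difference.

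**The case against.** The strongest reply is that the intended rule is easy to find. Two provisions address this case before Week 24, one by name in 7.4, and note m covers it generally. The conflicting sentence closes a paragraph that is largely about open-label eligibility and looks like a leftover. On ordinary reading, a specific and repeated rule governs a general one. I agree that the stay rule is probably the intended one. That does not dispose of the point: both 4.3.1 provisions have the same trigger, the conflicting one comes last, and it is mandatory where the stay rule only encourages.

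The second reply concerns consequence, and it stands. A reader might infer that the last sentence removes these subjects from the NT-proBNP test. The documents do not support that as a flat statement. Where the SAP does address off-drug data it leans towards on-treatment values: post-termination walks are excluded from the non-parametric 6MWD analysis, and LOCF in 8.6.2 carries forward the last valid on-treatment observation. If off-drug NT-proBNP is likewise not valid, a subject whose termination visit is by Day 127 is out of the ANCOVA under both rules and the contradiction costs nothing there. On the other side, SAP 10.2.2 states no exclusion of off-drug samples. The effect is possible, not established.

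It is also fair to say that vital status is still sought from subjects who leave (Protocol 15.7), and that nothing in the documents shows that any site followed the last sentence.

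**Conclusion.** The contradiction is real and sits in current operative text. It is wrong as written, and minor.

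The one clear analytic effect is on the 6MWD sensitivity analysis with post-termination data, which is not formally tested. It loses whatever off-drug walks the affected subjects would have attended, at most 4 each. Effects on the NT-proBNP ANCOVA and the 6MWD MMRM are conditional on off-drug values being meant to count and on attendance.

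Two stronger readings should be resisted. A reader might infer bias in the primary result, but the main primary analysis stops at drug discontinuation under either rule. A reader might also infer a material loss of Week 24 data, but the documents give no rate of second-therapy initiation before Week 24, so no count or share of affected subjects can be derived. Confidence is high for the conflict of wording and lower for any effect beyond the sensitivity analysis.

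**What to change.** Delete the last sentence of Protocol 4.3.1, or limit it to the period after Week 24, which the first paragraph after Table 4-1 already covers. Send sites a short letter saying that, before Week 24, a subject who starts a second oral PAH therapy stops study drug, completes the termination assessments and is encouraged to attend through Week 24. The open-label ineligibility statement is unaffected, because that earlier paragraph already contains it.

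The cost is one sentence and one letter. No visits, procedures or analyses are added beyond those already described.
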